12 WEEK POST TREATMENT EVALUATION: STUDY EFFICACY ENDPOINT ASSESSMENT

Twelve weeks following the completion of the 4-week treatment administration phase, the following will be recorded on the provided case report forms. These recordings will form the study endpoint data set from which change from baseline will be evaluated with respect to assessing study outcome.

- Review of adherence to medication and procedure use, and diet and exercise regime consistency since prior visit
- Digital Photographs
- Circumference measurements: waist and hips
- Global Aesthetic Improvement Scale (GAIS): Investigator and Subject
- Body Mass Index (BMI) Calculation
 - Height (in)
 - Weight (kg)
- Subject Satisfaction with Study Outcome
- Subject-Reported perception of Skin Tightness
- Adverse Events assessment

STATISTICAL ANALYSIS PLAN

STUDY POPULATIONS

The following two study populations will be evaluated:

1. Intent-to-Treat (ITT) Population

Primary analysis of efficacy will be according to the Intent to Treat (ITT) analysis, including all enrolled subjects.

Missing data for the ITT population will be handled through Last Observation Carried Forward (LOCF) methodology. Sensitivity analysis may be applied if missing data is extensive.

2. Per Protocol Population

Secondary analysis of efficacy to confirm the findings of the primary analysis will be conducted on the per protocol population, comprised of all subjects who completed the study per protocol through to the final treatment administration and outcomes measures recording visit, without incompletes or major protocol deviations or violations.

3. Safety Analysis Population

The Safety Analysis Population will comprise all subjects who were enrolled in the study.

BASELINE VARIABLES AND RECORDINGS

Descriptive summary data for the following baseline variables and recordings will be provided as numbers (n), mean, standard deviation (SD), median, and range (min., max.) for continuous variables and as number (n) and percentage (%) of the total number for categorical variables.

These variables include:

Subject demographics:

- age
- gender
- race
- ethnicity

Subject recordings:

- Baseline body weight (kg)
- Baseline height (m)
- Baseline Body Mass Index (BMI) in kg/m²
- Baseline waist and hip circumference measurements (ins.)

Medication and Procedures

- Current medications (OTC, prescription) taken for/with weight loss indications
- Prior medications (OTC, prescription) taken for/with weight loss indications

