All AEs that occur, including local and systemic reactions, not meeting the criteria for SAEs will be captured on the appropriate AE case report form (CRF). Information to be collected includes event description, time of onset, clinician's assessment of severity, relationship to study product (assessed only by those with the training and authority to make a diagnosis), corrective action taken, time of resolution/stabilization of the event and if the subject was withdrawn from the study because of the AE. Recording will be done in a concise manner using standard, acceptable medical terms.

All AEs occurring while on study must be documented appropriately regardless of relationship. All AEs will be followed to adequate resolution.

Any medical condition that is present at the time that the subject is screened will be considered as baseline and not reported as an AE. However, if the study subject's condition deteriorates at any time during the study, it will be recorded as an AE.

Changes in the severity of an AE will be documented to allow an assessment of the duration of the event at each level of severity to be performed. AEs characterized as intermittent require documentation of onset and duration of each episode.

The study investigator will record all reportable events with start dates occurring any time after informed consent is obtained until 7 (for non-serious AEs) or 30 days (for SAEs) after the last day of study participation.

Events will be followed for outcome information until resolution or stabilization.

ADVERSE EVENT REPORTING

Adverse Event Reporting Timeframes

The table below lists the minimum AE reporting requirements for study Investigators. Reporting of all safety events to the Sponsor will be completed through Investigator submission of the AE CRF and any applicable supporting documentation

Table 1: Investigator AE Reporting Requirements

Type of AE	Report to	Reporting Timeframe (from time of learning of event)
Adverse Event (AE)	IRB	Per IRB reporting requirements
	Sponsor	Within 10 working days
Serious Adverse Event (SAE)	Sponsor	Within 24 hours
	IRB	Per IRB reporting requirements
Device Deficiency	Sponsor	Within 48 hours
	IRB	If SAE occurs due to the device deficiency, within 24 hours of learning of the event and per IRB reporting requirements
Device Related AE/SAE	Sponsor	Within 24 hours

Unanticipated Adverse Device Effect (UADE) Reporting

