A protocol deviation is any noncompliance with the clinical trial protocol, ICH GCP, or Manual of Procedures (MOP) requirements. The noncompliance may be either on the part of the subject, the investigator, or the study site staff. As a result of deviations, corrective actions are to be developed by the site and implemented promptly.

These practices are consistent with ICH GCP:

- 4.5 Compliance with Protocol, sections 4.5.1, 4.5.2, and 4.5.3
- 5.1 Quality Assurance and Quality Control, section 5.1.1
- 5.20 Noncompliance, sections 5.20.1, and 5.20.2.

It is the responsibility of the site investigator to use continuous vigilance to identify and report deviations within 5 working days of identification of the protocol deviation, or within 5 working days of the scheduled protocol-required activity. All deviations must be addressed in study source documents (CRFs) and be reported to the sponsor. Protocol deviations must be sent to the reviewing IRB as applicable per their policies. The site investigator is responsible for knowing and adhering to the reviewing IRB requirements.

The investigator will not intentionally deviate from the study protocol procedures except in medical emergencies. Any and all protocol deviations that do occur will be recorded on the CRF and the IRB will be informed of the deviation, if applicable.

Protocol deviations will be recorded in CRFs and monitored for completion and accuracy during each monitoring visit.

SUBJECT SAFETY MONITORING

Subject safety data will be recorded in CRFs and monitored for completion and accuracy during each monitoring visit.

Subjects will be asked about any adverse events at the test site and are required to record any

potential adverse events in the Adverse Events Record Form and to notify the test site immediately. In such an occurrence, an unscheduled visit may be arranged so that the Investigator can clinically evaluate the findings. All adverse events will be recorded and reported as per the plan described in the relevant section above.

The Investigator can decide to stop the subject's participation in the study if he/she believes that subjects' participation is no longer safe.

The sponsor or the IRB may stop the research for the safety of the subjects if unreasonable risks to subjects persist.

PROTOCOL AMENDMENTS

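### A safety stop is written only as leaving the study, which shortens the window for new adverse events and leaves the 12-week photograph unprovided for

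*Combined protocol and SAP*

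**What the plan says.** Subject Safety Monitoring gives the investigator this option: "The Investigator can decide to stop the subject's participation in the study if he/she believes that subjects' participation is no longer safe". Adverse Event Recording uses the same unit: the form captures "if the subject was withdrawn from the study because of the AE". Neither section mentions a subject whose laser sessions end but who stays under observation.

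Adverse Event Recording also limits which events are recorded. The rule is "The study investigator will record all reportable events with start dates occurring any time after informed consent is obtained", and it runs "until 7 (for non-serious AEs) or 30 days (for SAEs) after the last day of study participation". The limit applies to start dates. For events that have already begun, the same section says "All AEs will be followed to adequate resolution" and "Events will be followed for outcome information until resolution or stabilization".

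The section on the time period for event assessment adds that adverse events are collected for the duration of the study. It does not say whether this covers a subject who has been stopped.

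The endpoint visit, with its photographs and adverse event assessment, is dated from the end of treatment: "Twelve weeks following the completion of the 4-week treatment administration phase, the following will be recorded on the provided case report forms". Under Study Populations, "Primary analysis of efficacy will be according to the Intent to Treat (ITT) analysis, including all enrolled subjects"; missing ITT data are filled by LOCF, and the safety population is also everyone enrolled.

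**The concern.** Read together, these rules let a decision about treatment also decide how long a subject is observed. A stop ends participation, and the end of participation starts the 7-day or 30-day limit on new events. The stopped subject still counts fully in the safety population, but late-onset events can be recorded for only part of the time available in a completer. These are subjects about whom the investigator already had a safety concern, so a short window for them is unhelpful in a trial of 35 people whose safety evidence is adverse event reporting.

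The primary endpoint is affected too. It needs a baseline and a 12-week image. After a stop, no text provides for the second image, so LOCF stands in for an observation that could often have been made.

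**Working it through.** **Inputs.** Treatment phase 4 weeks = 28 days (Treatment Administration Protocol). Endpoint visit 12 weeks = 84 days later (12 Week Post Treatment Evaluation). Stated study duration 16 weeks (Study Duration). Limits on new-event start dates 7 and 30 days (Adverse Event Recording). Enrolment 35 (Sample Size); success at 80% responders (Primary Efficacy Outcome).

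**1. The plan's own figure.** 28 + 84 = 112 days = 16 weeks, which matches the stated duration.

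**2. Completer.** With day 0 as consent and first treatment, new events are recorded to day 112 + 7 = 119 (non-serious) or 112 + 30 = 142 (serious). Counted from the end of treatment, this is 84 + 7 = 91 and 84 + 30 = 114 days.

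**3. Subject stopped on day d.** Assumption: the last day of participation is the day of the stop. Recording of new events then ends on day d + 7 or d + 30.

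| Participation ends | Non-serious, last day (share of completer) | Serious, last day (share of completer) |
|---|---|---|
| Day 0 | 7 (6%) | 30 (21%) |
| Day 14 | 21 (18%) | 44 (31%) |
| Day 28 | 35 (29%) | 58 (41%) |
| Day 112 (completer) | 119 | 142 |

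**4. Time after last exposure.** If the stop comes g days after the last session received, the windows are g + 7 and g + 30 days. At g = 0 they are 7 and 30, against 91 and 114 in a completer: ratios of 91/7 = 13 and 114/30 = 3.8. The gap narrows for later stops. At g = 42, halfway through follow-up, the windows are 49 and 72 days; at g = 84 there is no gap.

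**5. Photograph.** Success needs 0.80 × 35 = 28 responders. A stopped subject remains one of the 35, so one filled value can move the responder rate by at most 1/35 = 2.9 percentage points. A subject stopped after the treatment-end visit has that image available to carry forward. A subject stopped before it may have only the baseline image. The plan does not say how LOCF works for an image pair, which is a separate question.

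**6. With continued scheduled assessment.** The windows return to 119 and 142 days from first treatment, and the 12-week photograph is due. The sample size does not change.

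**The case against.** The strongest reply is that the protocol does not forbid ending laser sessions while the subject stays in the study. The option to end participation is permissive. Corrective action is recorded as an item distinct from withdrawal, and unscheduled visits are allowed. Adverse events are said to be collected throughout the study. The case report forms and consent form are appendices that were not available here, and they may carry a disposition item. This stands as far as it goes: the link between stopping treatment and leaving the study comes from what the text omits, and no section states it as a rule. It does not settle the matter, because the per-subject limit is explicit and the general collection statement does not say that it overrides that limit.

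Four stronger readings are tempting, and the documents do not support them.

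- *Subjects stopped for harm get the shortest safety follow-up overall.* Open events, including the one that led to the stop, are followed to resolution or stabilization, and each episode of an intermittent event is documented. Only detection of new-onset events is shortened.
- *The short window singles out harmed subjects.* Anyone who leaves early, for any reason, gets the same window.
- *The stopped subject drops out of the primary analysis.* The subject stays in the ITT set and LOCF applies.
- *The plan budgets for about five safety stops.* The 15% allowance, 35 enrolled for 30, is attrition from any cause. The plan regards adverse events as unlikely and gives no rate for safety stops.

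**Conclusion.** The point holds in a limited form. Followed as written, the rules cut new-event recording after last exposure to 7 days (non-serious) or 30 days (serious) for a subject stopped at a treatment session, against about 91 or 114 days in a completer. They also make no provision for that subject's 12-week photograph. The figures rest on three assumptions: the stop day is the last day of participation, which is undefined; the stop falls on the day of the last session received; and the completer's last session closes the 28-day phase.

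The 13-fold ratio compares observation windows. It is not an estimate of bias in the adverse event profile, whose size cannot be derived because the number of safety stops is unknown and may be small. The change is still worth making, since stated rules lead to avoidable loss of data and the remedy is cheap.

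**What to change.** Reconcile Subject Safety Monitoring, Adverse Event Recording, the section on the time period for event assessment, and the evaluation-visit and Study Populations sections, as follows.

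- Record *treatments discontinued* and *left the study* as separate dispositions, each with its own date, and define the last day of participation.
- State that subjects whose treatments are discontinued are asked to continue the scheduled treatment-end and 12-week assessments, including adverse event collection and photographs, unless consent is withdrawn or the investigator judges continued participation itself unsafe.
- For these subjects, run the 7-day and 30-day limits from the scheduled 12-week visit, and say how that date is set when the four weeks of treatment were not completed.

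When and why treatment is stopped stays with the investigator. The cost is about one protocol paragraph, a disposition item if the case report form lacks one, and a few already scheduled visits for subjects no longer being treated.
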